#### 4.5.4 Analysis of Primary and Secondary Efficacy Endpoints

For the primary efficacy endpoint, a one-sided 97.5% confidence interval for the difference in treatment group means (Mean [REDACTED] closure time *minus* the Mean closure time for conventional suture) will be constructed using the t-distribution. If the higher limit of the confidence interval is smaller than 0, then it will be concluded that [REDACTED] is considered to be superior to conventional suture.

The primary efficacy endpoint will be analyzed using the mITT and Per-Protocol analysis sets. The mITT analysis will be considered primary analysis. All secondary efficacy endpoints will be analyzed using the mITT analysis set.

All efficacy endpoints (see section 2.1) will be summarized descriptively by treatment group. The continuous variables will be summarized descriptively by number of subjects, mean, standard

deviation, minimum, and maximum. Categorical data will be summarized descriptively by frequencies along with the associated percentages. No inferential statistics will be generated for the secondary efficacy endpoints.

#### **4.5.5 Analysis of Secondary Safety Endpoints**

The incidence of adverse events (AEs) will be assessed at the preferred term level using the Medical Dictionary for Regulatory Activities (MedDRA) for event categorization. Incidence of AEs will also be assessed by 1) onset time (intraoperative or postoperative); 2) by relationship to study surgical procedure; 3) by relationship to the; and 4) by severity.

All safety endpoints (see section 2.2) will be summarized descriptively by treatment group for the Safety analysis set using available data. There will be no missing data imputation for the safety analysis. The continuous variables will be summarized descriptively by number of subjects, mean, standard deviation, minimum, and maximum. Categorical data will be summarized descriptively by frequencies along with the associated percentages. No inferential statistics will be generated for the safety endpoints.

### **4.6 Statistical/Analytical Issues**

#### **4.6.1 Handling of Dropouts or Missing Data**

All summaries of efficacy endpoints will be performed only on subjects who are randomized, and only observed data will be summarized. There will be no imputation for missing data or imputation of data for early terminated subjects.

#### **4.6.2 Multicenter Studies**

No adjustment for this multicenter study will be performed.

## **5.0 Risks and Benefits of the Study Device and Clinical Investigation**

The procedure being performed with the study suture and TSA are identical to the procedure subjects would receive as part of their standard of care procedure. To date, no risks have been reported with the study device beyond standard risks associated with TKA. This study may provide benefits on free wound closure device.

## **6.0 Adverse Event**

### **6.1 Definitions**

#### **6.1.1 Anticipated Adverse Events**

There are immediate post-operative events that are changes from the baseline condition of the Subject, but are expected events resulting from the surgery. If these events occur, they should be recorded in the Subject's medical record and reported forward as AEs to the study sponsor.

#### **6.1.2 Pre-existing Condition**

A pre-existing condition is one that is present at the start of the study, and is to be reported as part of the subject's medical history. It must be reported as a new Adverse Event if the intensity, frequency, or the character of the condition worsens during the study treatment.

To avoid confusing pre-existing conditions with AEs during data analysis, the study sites must make all attempts to provide start dates for all baseline medical conditions. Any pre-existing condition that has worsened in intensity, frequency, or the character of the condition should be recorded on the AE eCRF as an exacerbation of the pre-existing condition and the start date will be recorded as the time when the exacerbation occurred.

**Note:** Planned hospitalization for a pre-existing condition, or a procedure required by the study protocol, without serious deterioration in health, is not considered a serious adverse event.

#### **6.1.3 Adverse Event**

An AE is defined as any untoward medical occurrence, regardless of its relationship to the study device (study suture) or the study procedure (TKA). An untoward medical occurrence includes any new, undesirable medical experience or worsening of a pre-existing condition, which occurs at any point from the surgery to Final Visit.

#### **6.1.4 Expected Morbidity/Anticipated Adverse Events**

An expected morbidity/procedural complication is defined as an AE that is known to be common or usual in nature, severity, or incidence during TKA in patients with knee osteoarthritis or other diseases.

Postoperative pain and fever is expected and will not be documented as an adverse event unless the Investigator considers the pain or fever to exceed that normally anticipated following a TKA procedure.

#### **6.1.5 Serious Adverse Event**

A Serious Adverse Event (SAE) is any AE that:

- led to a death,
- led to a serious deterioration in the health of the subject that either resulted in:
  - a congenital deformity or abnormality;
  - a life-threatening illness or injury;
  - a permanent impairment of a body structure or a body function;
  - in-patient hospitalization or prolongation of existing hospitalization;
  - medical or surgical intervention to prevent life-threatening illness or injury; or
  - permanent impairment of a body structure or a body function.

**Note:** “Death” should not be reported as an AE. The cause of death should be reported as the AE. The only exception is “Sudden Death” when the cause is unknown.

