#### **6.1.7 Serious Adverse Device Effect (SADE)**

A serious adverse device effect is an adverse device effect that has resulted in any of the consequences characteristic of a serious adverse event or that might have led to any of these consequences if suitable action had not been taken or intervention had not been made or if circumstances had been less opportune.

Note: Anticipated serious adverse device effect (ASADE) is an effect which by its nature, incidence, severity or outcome has been identified in the risk analysis report.

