### **6.3 Reporting Serious Adverse Events**

All of the serious adverse event must be reported to the sponsor as well as China Food and Drug Administration and local ethics committee by the site immediately (within 24 hours) after the site becomes aware of the information by entering the data into the AE eCRF.

The Sponsor will report any suspected serious adverse events to the regulatory authorities (including CFDA), within the required timeframes of five working days for SAEs that are fatal, and fifteen working days for all other SAEs. Given the observational nature of this study, the Sponsor will not monitor or enforce adherence to CFDA reporting for non-[REDACTED] products.

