5. Incidence of wound closure related adverse events and serious adverse events;

Table 2: ASEPSIS Score

Wound Characteristic	Proportion of Wound Affected					
	0	<20	20-39	40-59	60-79	>80
Serous Exudate	0	1	2	3	4	5
Erythema	0	1	2	3	4	5
Purulent Exudate	0	2	4	6	8	10
Separation of Deep Issue	0	2	4	6	8	10
Points are scored for daily wound inspection.						
Additional Treatment		Points				
Antibiotics		10				
Drainage of Pus under local anesthesia		5				
Debridement of Wound (General Anesthesia)		10				
Serous Discharge*		Daily 0-5				
Erythema*		Daily 0-5				
Purulent Exudate*		Daily 0-10				
Separation of Deep Tissues*		Daily 0-10				

Isolation of Bacteria	10
Stay as In-patient Prolonged Over 14 Days	5

*Given scores on 5 of 7 days and the highest weekly score used.

Category of Infection	
Total Score**	Definition
0-10	Satisfactory Healing
11-20	Disturbance of Healing
20-30	Minor Wound Infection
31-40	Moderate Wound Infection
>40	Severe Wound Infection

**Total Score calculated adding scores for individual wound characteristics and additional treatment.

Table 3: Acute Inflammatory Response Evaluation (AIRE) Score

Score	Erythema	Oedema	Pain	Temperature
0	None observed	None observed	None	None
1	Slight blanching redness along incision closure line	Slight increase in tissue firmness (turgor)	Pain at site with pressure	Slightly warmer compared to adjacent skin
2	Moderate redness extending < 2 mm	Pitting of skin around incision with touch	Pain at site with touch	Definitely warmer compared to adjacent skin
3	Intense redness extending > 2 mm	Tense firmness of skin around incision	Continuous pain	Radiating heat at incision site

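### The SAE definition in Protocol 6.1.5 repeats one criterion and leaves out intervention to prevent permanent impairment, a narrow gap in SAE classification and 24-hour reporting

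*Protocol*

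**What the plan says.** Protocol 6.1.5 makes an adverse event serious if it led to death, or if it "led to a serious deterioration in the health of the subject that either resulted in" one of six listed outcomes. The third is "a permanent impairment of a body structure or a body function". The fourth is "in-patient hospitalization or prolongation of existing hospitalization". The fifth is the intervention criterion, "medical or surgical intervention to prevent life-threatening illness or injury", which ends with a semicolon and the conjunction *or*. The sixth then repeats the third, without its opening article.

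Protocol 6.1.7 defines a serious adverse device effect more widely. It includes a device effect that "might have led to any of these consequences if suitable action had not been taken or intervention had not been made".

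Protocol 6.3 requires sites to report SAEs to the sponsor, the regulator and the ethics committee "immediately (within 24 hours) after the site becomes aware of the information by entering the data into the AE eCRF". It does not name serious adverse device effects.

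The SAP has no SAE definition of its own, so 6.1.5 governs its tables. SAP 1.2.3 lists as a safety endpoint "Incidence of wound closure related adverse events and serious adverse events", and SAP 3.3.2.1 tabulates SAEs by system organ class and preferred term in each arm.

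**The concern.** The sixth sub-bullet does nothing as a criterion in its own right, because the third already says the same. It makes sense only as a second object of the verb in the fifth, that is, intervention to prevent either a life-threatening condition or permanent impairment. Set as a separate bullet, it leaves the second half of that criterion unstated.

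At stake are the seriousness label and what hangs on it. SAE status is what triggers the 24-hour site report, and SAEs related to wound closure are a named safety endpoint. No interim analysis or data monitoring committee is planned (SAP 4.1 and 4.2), so prompt SAE reporting matters for safety oversight while the trial runs. Sites that read the list literally and sites that guess its intent could classify like events differently.

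**Working it through.** No arithmetic applies. The check is to count the criteria and run test events through them.

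**Count.** The six sub-bullets are: congenital deformity or abnormality; life-threatening illness or injury; permanent impairment; hospitalization or its prolongation; intervention to prevent a life-threatening condition; permanent impairment again. That is six bullets and five distinct criteria. Intervention to prevent permanent impairment is in none of them.

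**Test events.** Each is a wound event treated by an intervention that succeeds in preventing permanent impairment. None is fatal or life-threatening.

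| Event | 6.1.5 as written | With the last two bullets merged |
|---|---|---|
| A. Serious deterioration; treated as an outpatient, or in the index stay without lengthening it | Meets no criterion | SAE (intervention) |
| B. As A, but admitted or stay prolonged | SAE (hospitalization) | SAE |
| C. No serious deterioration; no admission or prolongation | Not an SAE (fails the lead-in) | Not an SAE |

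Only event A changes, and that is the whole extent of the gap.

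**Does another provision catch event A?**

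- Protocol 6.1.7 does, as a class, if the event is judged a device effect. But 6.3 ties the 24-hour report to SAEs, and the SAP plans no table of serious adverse device effects.
- Protocol 6.2 puts every adverse event on the AE eCRF, so the event is recorded. It states no 24-hour site deadline for non-serious events.
- Protocol 7.2 has a 24-hour rule, but for product complaints. By 7.1 these are alleged product deficiencies, not wound events as such.
- Protocol 2.3 and SAP 3.3 summarize SSI, dehiscence requiring intervention and delayed healing whatever the SAE status. These are end-of-study summaries and trigger no expedited report.

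None of these supplies the missing SAE criterion. Several limit what is lost by its absence.

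**The case against.** The case for leaving the text alone has real force.

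*The hospitalization criterion already covers most of this.* A reader might infer from the gap that re-closing or washing out a wound over the prosthesis is never an SAE. The documents do not support that. An event with serious deterioration that leads to admission or a longer stay is serious whatever the intervention was for.

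*The lead-in limits both the gap and the remedy.* A bedside or clinic re-closure without serious deterioration is not an SAE now, and would not become one after the merge. This stands.

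*Nothing is hidden.* A reader might infer that wound events would be lost from the trial. They would not. They are recorded as adverse events, tabulated by severity and device relationship, listed (SAP 3.3.2), and counted under the separate wound endpoints where those apply. The safety analysis is descriptive throughout. What is exposed is the seriousness label and the speed of reporting.

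*Section 6.1.7 does not contradict 6.1.5.* It is tempting to say that the same averted harm is serious or not depending on an unblinded surgeon's causality call. But 6.1.7 is a wider test for device effects only, and the merge would not remove that difference. An averted hospitalization, for example, would still count only when it is a device effect. Section 6.1.7 shows that the protocol regards averted permanent impairment as serious in that setting. It does not show a conflict.

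*The break could be an artefact of PDF conversion.* A wrapped line can look like a new bullet. But a line wrap would not add the semicolon before the conjunction, so a drafting break is the likelier explanation.

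*Investigators may read it as intended.* Some will. A definition that triggers a 24-hour report should not depend on that.

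**Conclusion.** The definition is wrong as written, in a limited way. One criterion appears twice and another is missing. An event with serious deterioration that needed intervention to prevent permanent impairment falls outside the literal SAE definition if it brought no admission, prolonged stay, life threat or lasting impairment. It can then miss the SAE tables and the 24-hour report.

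The size of the undercount cannot be given, because the documents state no rate for such events and no expected number of SAEs. A reader might note that one subject in a planned arm of 92 is 1/92 = 1.1 percentage points and infer that a few omissions would remove most of the serious wound events. The first is only a unit conversion. The second needs counts that the documents do not give.

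The conclusion assumes that sites apply the bullets literally and that the bullet break is in the protocol itself. The primary endpoint, its analysis and the sample size are unaffected.

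**What to change.** Merge the last two sub-bullets of Protocol 6.1.5 into one, which would read "medical or surgical intervention to prevent life-threatening illness or injury", or to prevent "a permanent impairment of a body structure or a body function". Keep the third sub-bullet, so that impairment that does occur remains a criterion in its own right. Leave the lead-in and the hospitalization criterion as they are, and carry the same wording into the eCRF completion guidance.

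The SAP needs no edit, since its SAE tables take their definition from the protocol. The cost is a one-line protocol change and the matching line of eCRF guidance. SAE counts may rise slightly. No treatment, assessment or planned table changes.

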#### **6.1.6 Adverse Device Effect (ADE)**

An Adverse Device Effect is any untoward and unintended response to a medical device. This includes any event arising from insufficiencies or inadequacies in the Instructions for Use or the deployment of the device. It also includes any event that is a result of user error.

#### **6.1.7 Serious Adverse Device Effect (SADE)**

A serious adverse device effect is an adverse device effect that has resulted in any of the consequences characteristic of a serious adverse event or that might have led to any of these consequences if suitable action had not been taken or intervention had not been made or if circumstances had been less opportune.

Note: Anticipated serious adverse device effect (ASADE) is an effect which by its nature, incidence, severity or outcome has been identified in the risk analysis report.

#### **6.1.8 Severity of Adverse Events**

It is the Investigator's responsibility to assess the severity of an AE. A change in severity may constitute a new reportable AE.

The following guideline should be used to determine the severity of each adverse event:

- **MILD:** Awareness of experience, but easily tolerated. No medical intervention required.
- **MODERATE:** Enough discomfort to interfere with usual activities. Medical intervention required.
- **SEVERE:** Inability to carry out usual activities. Medical intervention (including hospitalization or prolongation of hospitalization) required.

#### **6.1.9 Relationship of Adverse Events**

It is the Investigator's responsibility to assess the relationship of an AE to the study procedure (TKA) and study device.

The following guidelines should be used in determining the relationship of an adverse event to the study device, study procedure, or other causality:

- **NOT RELATED:** The event is due to extraneous causes.
- **POSSIBLY RELATED:** The event is unlikely associated, but cannot be ruled out with certainty.
- **PROBABLY RELATED:** The event is likely associated, but another cause cannot be ruled out with certainty.
- **DEFINITELY RELATED:** The event is associated with a high degree of certainty; or
- **UNKNOWN:** The event cannot be defined by the categories listed above.

### **6.2 Reporting Adverse Events**

Investigators are required to report all AEs experienced by subjects from the time of enrollment (defined as first incision) until the subject completes the study or terminates early. All AEs, regardless of their relatedness to the study device, must be reported in the AE eCRF. The investigator will evaluate the intensity of the event, severity of the event, and its relatedness to the study device or procedure,. Any necessary medical management of the event will be recorded in the subject's medical record/source document. All AEs must be followed until resolution or until they become stable but ongoing.

The sponsor will follow CFDA's guideline to request sponsor to report the safety events including SAE/AE with timeline, which is regulated by law.

### **6.3 Reporting Serious Adverse Events**

All of the serious adverse event must be reported to the sponsor as well as China Food and Drug Administration and local ethics committee by the site immediately (within 24 hours) after the site becomes aware of the information by entering the data into the AE eCRF.

The Sponsor will report any suspected serious adverse events to the regulatory authorities (including CFDA), within the required timeframes of five working days for SAEs that are fatal, and fifteen working days for all other SAEs. Given the observational nature of this study, the Sponsor will not monitor or enforce adherence to CFDA reporting for non-[REDACTED] products.

## **7.0 Product Complaints**

### **7.1 Product Complaints Definition**

A product complaint is defined as any written, electronic or oral communication that alleges

deficiencies related to the identity, labeling, quality, durability, reliability, safety, effectiveness, or performance of a device (i.e., Barbed suture) after it is release for distribution (policy of Johnson and Johnson Medical Device Quality management). A product complaint may or may not be associated with an AE/SAE.

Product complaints may include, but are not limited to:

- a) Product contamination;
- b) Defective components;
- c) Poor packaging or product mix-up;
- d) Device malfunction, which is the failure of a device to perform as intended for this study;
- e) Labeling concerns
- f) User errors.

## **7.2 Reporting Product Complaints**

All product complaints related to the study (barbed suture/TSA/traditional suture) shall be documented throughout the clinical investigation.

Product complaints related to the study (barbed suture/TSA/traditional suture) must be reported to the Sponsor in a timely manner and no later than 24 hours after becoming aware of the event.

The Product Complaint Form must be faxed to China CHU at the following [REDACTED]. One copy of the processed form should be kept on-site with the device concerned, and the device should be retained. [REDACTED] and /or [REDACTED] representatives will organize collection of the device for evaluation.

## **7.3 Reporting Product Complaints for Non-[REDACTED] Devices**

In compliance with the requirements of local regulations, describing the handling of product complaints, the study site must report all product complaints of other (non-[REDACTED]) marketed products/devices used in this study (e.g., knee prosthesis).

4	INTERIM ANALYSIS AND DATA MONITORING COMMITTEE (DMC).....	24
4.1	INTERIM ANALYSIS	24
4.2	DATA MONITORING COMMITTEE	24
5	SUMMARY OF MAJOR CHANGES IN THE PLANNED ANALYSES.....	24
6	REFERENCES.....	24
7	ATTACHMENT.....	25

ABBREVIATIONS

Abbreviation	Term
ADE	Adverse Device Effect
AE	Adverse Event
AIRE	Acute Inflammatory Response Evaluation
ASADE	Anticipated Serious Adverse Device Effect
BMI	Body Mass Index
CDC	Centers for Disease Control
CFDA	China Food and Drug Administration
CFR	Code of Federal Regulations
CHU	Complaint Handling Unit
EC	Ethics Committee
eCRF	Electronic Case Report Form
ESC	Surgical Care
EDC	Electronic Data Capture
FPG	Fasting Plasma Glucose
GCP	Good Clinical Practice
ICD	Informed Consent Document
mITT	Modified Intent-to-Treat
IVRS	Interactive Voice Response System
IWRS	Interactive Web Response System
MedDRA	Medical Dictionary for Regulatory Activities
OR	Operating Room
PI	Principal Investigator
PT	Preferred Term
PP	Per-Protocol
QoL	Quality of Life
ROM	Range of Motion
SADE	Serious Adverse Device Effect
SAE	Serious Adverse Event
SAP	Statistical Analysis Plan
SOC	System Organ Class
SSI	Surgical Site Infection
TKA	Total Knee Arthroplasty

Abbreviation	Term
TSA	Topical Skin Adhesive
USP	United States Pharmacopeia
VAS	Visual Analogue Scale

1 INTRODUCTION

The purpose of this statistical analysis plan (SAP) is to describe the procedures and the statistical methods that will be used to analyze and report results for Protocol <ESC-16-001> Administrative Change 1 (27 May 2017).

1.1 STUDY OBJECTIVES

1.1.1 Primary Objective(s)

The primary objective of this prospective, randomized controlled study is to evaluate the wound closure efficiency of [REDACTED] compared to conventional sutures in patients undergoing Total Knee Arthroplasty (TKA). For the purpose of this study, wound closure efficiency is defined as the total time required to close the surgical incisions in patients undergoing TKA procedures using [REDACTED] compared to those using traditional sutures.

